8.1.5. Analyses of time-to-event data

Kaplan-Meier plots will be presented for time-to-event data. Event-free patients will be censored at the end of their observation period or 60 weeks after the start of treatment, whichever came first. If the time to event exceeds 60 weeks, the patient will be treated as event-free and censored at 60 weeks. For malignancy, however, no such upper limit will be set for the time to onset, and malignancy-free patients will be censored at the end of their observation period.

8.2. Statistical Analyses

8.2.1. Patient description

• Summarization of Participating Sites and Patients by Type of Site

Using data from CRF-collected patients, sites and patients will be summarized in terms of n and proportion by type of site, with possible types defined below:

- National, public, or private university hospital
- National hospital established by the Ministry of Health, Labour and Welfare (MHLW)
- Prefectural or municipal hospital
- Public institution
- Hospital other than the four types above that has been established by a corporation or individual
- Clinic or practice

In addition, the mean, minimum, and maximum number of patients per site will be presented.

• Constitution of patients

Using data from registered patients, the number of registered patients, observation-completed patients, patients included in the SAS (including the numbers by mean daily dose), patients treated for a long term (including subgroups by mean daily dose) and patients included in the EAS will be presented. In addition, the number of CRF-uncollected patients, patients excluded from the SAS, patients excluded from the SAS for each category of reason for exclusion, patients excluded from the EAS, and patients excluded from the EAS for each category of reason for exclusion will be presented.

• Completion of treatment or reason for discontinuation

Using the SAS (including the subgroups by mean daily dose), set of patients treated for a long term (including the subgroups by mean daily dose), and EAS, patients who discontinued the treatment with this

drug will be summarized in terms of n and proportion by time of discontinuation [≤ 8 weeks, > 8 to ≤ 16 weeks, > 16 to ≤ 26 weeks, > 26 to ≤ 60 weeks, > 60 weeks], and patients who completed the treatment with this drug will be summarized in terms of n and proportion. In addition, patients who discontinued the treatment will be summarized in terms of n and proportion by reason for discontinuation.

Listing of patients excluded from analyses

Patients excluded from the SAS will be listed in tabular form with their reason for exclusion. Similarly, patients excluded from the EAS will be listed in tabular form with their reason for exclusion.

8.2.2. Patient characteristics and medical history

• Patient characteristics

Using the SAS (including subgroups by mean daily dose), set of patients treated for a long term (including subgroups by mean daily dose), and EAS, patients will be, according to the methods described in Section 8.1, summarized with respect to the following patient characteristics:

- Gender [male, female]
- Age (continuous)
- Age [<15 years, ≥15 to <65 years, ≥65 years]
- Age [<50 years, \ge 50 to <65 years, \ge 65 years]
- Body weight (continuous)
- Body weight [$<50 \text{ kg}, \ge 50 \text{ to } <60 \text{ kg}, \ge 60 \text{ to } <70 \text{ kg}, \ge 70 \text{ kg}$]
- BMI (continuous)
- BMI [<18.5, ≥ 18.5 to <25, ≥ 25]
- Diagnosis [ulcerative colitis, other]
- Duration of UC (continuous)
- Duration of UC [<2 years, ≥ 2 to <5 years, ≥ 5 to <10 years, ≥ 10 to <20 years, ≥ 20 years]
- Range of UC [pancolitis, left-sided disease, proctitis, right-sided or segmental disease, other]
- Severity of UC [mild, moderate, severe]
- Refractory UC based on treatment responsiveness [absent, present]
- Refractory UC based on treatment responsiveness [absent, steroid-resistant, steroid-dependent, present but not steroid-resistant or steroid-dependent]
- Past history [absent, present]
- Infections [absent, present]
- Past history of malignancy [absent, present]
- Past history of an autoimmune disease [absent, present]
- Past history of a cardiovascular disease [absent, present]
- Past history of lung disorder [absent, present]
- Past history of gastrointestinal disorder [absent, present]
- Past history of hepatic function disorder [absent, present]
- Hepatic function disorder: past history of hepatitis B [absent, present]
- Hepatic function disorder: past history of hepatitis C [absent, present]
- Hepatic function disorder: past history of hepatitis B virus carrier [absent, present]

- Hepatic function disorder: past history of hepatitis C virus carrier [absent, present]
- Past history of renal impairment [absent, present]
- Past history of metabolic abnormality [absent, present]
- Metabolic abnormality: past history of diabetes mellitus [absent, present]
- Past history of anaemia [absent, present]
- Complications [absent, present]
- Complication of an infection [absent, present]
- Complication of malignancy [absent, present]
- Complication of an autoimmune disease [absent, present]
- Complication of a cardiovascular disease [absent, present]
- Complication of lung disorder [absent, present]
- Complication of gastrointestinal disorder [absent, present]
- Complication of hepatic function disorder [absent, present]
- Complication of hepatic function disorder: hepatitis B [absent, present]
- Complication of hepatic function disorder: hepatitis C [absent, present]
- Complication of hepatic function disorder: hepatitis B virus carrier [absent, present]
- Complication of hepatic function disorder: hepatitis C virus carrier [absent, present]
- Complication of renal impairment [absent, present]
- Complication of metabolic abnormality [absent, present]
- Complication of metabolic abnormality: diabetes mellitus [absent, present]
- Complication of anaemia [absent, present]
- Smoking [non-smoker, former smoker, present smoker, unknown]
- Family history of malignancy (including lymphoma) [absent, present, unknown]
- Family history of malignancy (including lymphoma) [absent, present (colorectal cancer absent),
 present (colorectal cancer present), present (colorectal cancer unknown), unknown]
- Prior treatment with a biologic agent [absent, present, unknown]
- Prior treatment with a biologic agent [absent, infliximab, adalimumab, golimumab, other, unknown]
- Effectiveness of prior biologics (no prior use, 1st line ineffective, 2nd line ineffective, prior use unknown)
- Baseline partial Mayo score (continuous)
- Baseline Mayo score (continuous)
- Baseline Mayo score [<6, ≥6]
- Baseline stool frequency subscore [0, 1, 2, 3]
- Baseline rectal bleeding subscore [0, 1, 2, 3]
- Baseline findings of flexible sigmoidoscopy subscore [0, 1, 2, 3]
- Baseline physician's global assessment subscore [0, 1, 2, 3]
- Baseline faecal calprotectin [≤50 mg/kg, >50 to ≤300 mg/kg, >300 mg/kg, not tested]
- Starting daily dose of Xeljanz [5 mg, 10 mg, 15 mg, 20 mg, >20 mg]
- Prior treatment with a 5-aminosalicylic acid preparation [absent, present]
- Prior treatment with steroid [absent, present]
- Prior treatment with azathioprine [absent, present]
- Prior treatment with 6-mercaptopurine [absent, present]

- Prior treatment with an immunomodulator (azathioprine or 6-mercaptopurine) [absent, present]
- Prior treatment with tacrolimus [absent, present]
- Prior treatment with infliximab [absent, present]
- Prior treatment with adalimumab [absent, present]
- Prior treatment with golimumab [absent, present]
- Prior vaccination with a herpes zoster vaccine [absent, present]
- Prior vaccination with a pneumococcal vaccine [absent, present]
- Prior vaccination with a tuberculosis vaccine [absent, present]
- Prior vaccination with a pneumocystis jirovecii pneumonia vaccine [absent, present]
- Prior vaccination with a hepatitis B vaccine [absent, present]
- Prior treatment with a non-drug therapy [absent, present]
- Prior treatment with a non-drug therapy: blood cell component removal therapy [absent, present]
- Prior treatment with a non-drug therapy: surgery [absent, present]
- Baseline neutrophil count [<2000/μL, ≥2000/μL, not tested]
- Baseline lymphocyte count [<1000/μL, ≥1000/μL, not tested]
- Baseline hemoglobin [$\leq 8 \text{ g/dL}$, $\geq 8 \text{ g/dL}$, not tested]

Using the SAS, patients will be summarized according to the following factors in terms of n and proportion by SOC and PT:

- Past history (diseases and syndromes recorded as past history in the CRF entry "Medical history")
- Complications (diseases and syndromes recorded as present illness in the CRF entry "Medical history")

Using the SAS, patients will be summarized according to the following factors in terms of n and proportion:

- Pre-treatment testing for hepatitis virus [absent, present]
- Pre-treatment HBs antigen test [positive, negative, not tested]
- Pre-treatment HBs antibody test [positive, negative, not tested]
- Pre-treatment HBc antigen test [positive, negative, not tested]
- Pre-treatment HCV antibody test [positive, negative, not tested]
- Pre-treatment imaging [absent, present]
- Pre-treatment imaging: chest X-ray [normal, abnormal, not tested]
- Pre-treatment imaging: chest CT [normal, abnormal, not tested]
- Pre-treatment interferon gamma release assay [absent, present]
- Pre-treatment interferon gamma release assay: QuantiFERON [positive, equivocal, negative, indeterminate, not tested]
- Pre-treatment interferon gamma release assay: T-Spot. TB [positive, equivocal, negative, indeterminate, not tested]
- Pre-treatment tuberculin reaction [-, 1+, 2+, 3+, indeterminate, not tested]
- Pre-treatment diastolic blood pressure [<60 mmHg, ≥60 to <80 mmHg, ≥80 to <100 mmHg,
 ≥100 to <120 mmHg, ≥120 mmHg, not measured]

Pre-treatment systolic blood pressure [<120 mmHg, ≥120 to <140 mmHg, ≥140 to <160 mmHg,
 ≥160 to <180 mmHg, ≥180 mmHg, not measured]

Using the SAS and EAS, a breakdown of patients by each of the following factors will be presented in terms of n and proportion. Concomitant medications and non-drug therapies will be defined in align with the data collection period for adverse reactions and AEs so that relationship to adverse reactions and AEs can be assessed.

- Concomitant medications (drugs recorded in the CRF entry "Drug therapies for UC prior treatment and concomitant therapies" that were used in the period from the start of the treatment with this drug to the discontinuation of treatment or 60 weeks after the start of treatment, whichever came first)
- Non-drug therapies (non-drug therapies recorded in the CRF entry "Non-drug therapies for UC prior treatment and concomitant therapies" that were used in the period from the start of the treatment with this drug to the discontinuation of treatment or 60 weeks after the start of treatment, whichever came first)
- Prior medications (medications recorded in the CRF entry "Past history of treatment for UC biological therapeutics", and medications recorded in the CRF entry "Drug therapies for UC prior treatment and concomitant therapies" of which administration had been started by the day before the start of the treatment with this drug)

• Dosing status of Xeljanz tablets

Using the SAS (including the subgroups by mean daily dose) and the set of patients treated for a long term (including the subgroups by mean daily dose), dosing data for this drug will be summarized with respect to the following aspects:

- Starting daily dose [5 mg, 10 mg, 15 mg, 20 mg, >20 mg]
- Duration of treatment [\leq 15 weeks, >15 to \leq 30 weeks, >30 to \leq 45 weeks, >45 to \leq 60 weeks, >60 to \leq 75 weeks, >75 to \leq 90 weeks, >90 to \leq 105 weeks, >105 to \leq 120 weeks, >120 to \leq 135 weeks, >135 weeks]
- Total duration of treatment (patient-years) [≤15 weeks, >15 to ≤30 weeks, >30 to ≤45 weeks, >45 to ≤60 weeks, >60 to ≤75 weeks, >75 to ≤90 weeks, >90 to ≤105 weeks, >105 to ≤120 weeks, >120 to ≤135 weeks, >135 weeks] (The total duration of treatment in each category and the accumulated total duration of treatment will be presented.)
- Mean daily dose by duration of treatment (mg) (summary statistics) [<15 mg, ≥15 mg] [<17 mg,
 ≥17 mg], with the following categories for the duration of treatment:
 - Any duration of treatment
 - Duration of treatment ≤15 weeks
 - Duration of treatment > 15 to ≤ 30 weeks
 - Duration of treatment >30 to <45 weeks
 - Duration of treatment >45 to ≤ 60 weeks
 - Duration of treatment >60 to ≤ 75 weeks
 - Duration of treatment >75 to ≤90 weeks

• Duration of treatment >90 to <105 weeks

- Duration of treatment >105 to <120 weeks
- Duration of treatment >120 to ≤135 weeks
- Duration of treatment >135 weeks

The duration of treatment is defined as the period from the start date of the treatment with this drug to the last observed administration date of this drug, including non-dosing days.

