7.3.5. Status of vaccination

The record of vaccines given in relation to the treatment of ulcerative colitis should include the following information from baseline to the date of completion of the observation period (or date of XELJANZ discontinuation).

- 1. Herpes zoster vaccine: Status and date of vaccination, drug name (vaccine name)
- 2. Pneumococcal vaccine: Status and date of vaccination

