7.3.6. Status of prophylactic treatment

The record of the status of prophylactic treatment given from 3 months before the commencement of XELJANZ treatment to the date of completion of the observation period (or date of XELJANZ discontinuation) should include the following information.

- 1. Classification: Tuberculosis, Pneumocystis jirovecii pneumonia, hepatitis B
- 2. Drug name (product name)
- 3. Duration of treatment

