6.4. Covariates

Candidate covariates for the development of Serious infections (including Tuberculosis, Pneumonia, Pneumocystis pneumonia, Sepsis, and Opportunistic infection), Herpes zoster, and Malignancy considered in this study are shown below.

| Covariate | Serious infections | Herpes zoster | Malignancy |
|--------------------------------------|-----------------------|------------------|------------|
| Gender [reference: male] | 0 | 0 | 0 |
| Age [reference: <50 years] | 0 | 0 | 0 |
| Body weight [reference: <50 kg] | 0 | 0 | 0 |
| BMI [reference: <18.5 kg] | 0 | 0 | 0 |
| Duration of UC [reference: <2 years] | 0 | 0 | 0 |

NIS Protocol A3921248 Statistical Analysis Plan

Serious Herpes Covariate infections Malignancy zoster Severity of UC [reference: moderate] 0 Past history (Infections) [reference: absent] 0 0 Past history (Malignancy) [reference: absent] × X Past history (Lung disorder) [reference: absent] 0 × × Complications (Infections) [reference: absent] 0 0 X Complications (Malignancy) [reference: absent] 0 Complications (Hepatic function disorder) [reference: absent] 0 0 0 Complications (Hepatitis B) [reference: absent] X X 0 Complications (Hepatitis C) [reference: absent] X X 0 Complications (Renal impairment) [reference: absent] 0 \circ 0 Complications (Diabetes mellitus) [reference: absent] Ο 0 0 Smoking [reference: absent] 0 0 0 Family history of malignancy (including lymphoma) [reference: absent] Prior treatment with a 5-aminosalicylic acid preparation [reference: 0 0 0 absent] Prior treatment with steroid [reference: absent] 0 0 0 Prior treatment with an immunomodulator (azathioprine, 0 0 6-mercaptopurine) [reference: absent] Prior treatment with tacrolimus [reference: absent] Prior treatment with a biologic agent [reference: absent] 0 0 Baseline neutrophil count [reference: <2000/µL] 0 0 0 Baseline lymphocyte count [reference: <1000/μL] 0 0 \circ Prior vaccination with a herpes zoster vaccine [reference: absent] 0 0 × Prior vaccination with a pneumococcal vaccine [reference: absent] 0 Prior vaccination with a tuberculosis vaccine [reference: absent] 0 Prior vaccination with a pneumocystis jirovecii pneumonia vaccine [reference: absent] Prior vaccination with a hepatitis B vaccine [reference: absent]

o: Applied, ×: Not applied

Additional covariates may be included or some deleted after consideration based on an interim analysis of this study or emerging knowledge. If this will occur, this SAP will be revised.

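### SAP 6.4 and 8.2.2 label three factors as prior vaccination, but the protocol collects them only as prophylactic drug treatment, so as written they have no data source and prophylaxis has no named analysis

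*SAP*

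**What the plan says.** **Protocol.** Section 7.3.5 has two vaccination items: "Herpes zoster vaccine: Status and date of vaccination, drug name (vaccine name" and "Pneumococcal vaccine: Status and date of vaccination". Footnote 5 to Table 2 names the same two vaccines and no others. Section 7.3.6 is a separate record of prophylactic treatment with three categories, "Classification: Tuberculosis, Pneumocystis jirovecii pneumonia, hepatitis B", plus drug name and duration. Its window opens 3 months before the first dose and closes at the end of observation or at discontinuation.

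**SAP.** Section 8.2.2 lists prior vaccination against herpes zoster and pneumococcus, followed by "Prior vaccination with a tuberculosis vaccine [absent, present", "Prior vaccination with a pneumocystis jirovecii pneumonia vaccine [absent, present" and "Prior vaccination with a hepatitis B vaccine [absent, present". Section 6.4 carries the same five as candidate covariates, for example "Prior vaccination with a tuberculosis vaccine [reference: absent" and "Prior vaccination with a hepatitis B vaccine [reference: absent".

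**Use of the factors.** Section 5.4.2 makes the 8.2.2 characteristics safety subgroup factors. Section 8.2.3.3 uses them for risk ratios on each element of the safety specification, where events developed in at least 10 patients.

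**The concern.** The three doubtful factors relate to infections that the study is meant to watch. Hepatitis B reactivation is an important identified risk in its own right. Tuberculosis and Pneumocystis pneumonia are named inside the serious-infection risk. The sponsor collects prophylaxis against exactly these three diseases, yet no SAP factor, covariate, subgroup or table carries that name.

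Two things are at stake. A programmer who follows the SAP text has no protocol-defined field from which to build the three factors. A reader of the final report, which supports the re-examination application (SAP 3), could take a prophylactic drug course for a vaccination. Two genuine vaccination factors stand directly above the doubtful ones, so nothing in the output would give the error away.

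**Working it through.** No arithmetic beyond a count applies. The check sets the protocol's data items against the SAP's factors.

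| Disease | Protocol vaccination item (7.3.5) | Protocol prophylaxis item (7.3.6) | SAP label (6.4 and 8.2.2) |
|---|---|---|---|
| Herpes zoster | yes | no | prior vaccination |
| Pneumococcus | yes | no | prior vaccination |
| Tuberculosis | no | yes | prior vaccination |
| Pneumocystis pneumonia | no | yes | prior vaccination |
| Hepatitis B | no | yes | prior vaccination |

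1. **Count.** Five factors are labelled vaccination and two have a vaccination item in the protocol, so 5 − 2 = 3 do not. Each of the three appears in two SAP sections, so 3 × 2 = 6 lines are affected.

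2. **Does prophylaxis enter by another route?** The concomitant and prior medication tables in SAP 8.2.2 draw on the CRF entries for UC drug therapies and for past biologics. Prophylactic drugs recorded under 7.3.6 are in neither. The only similar word in the SAP is a MedDRA preferred term for COVID-19 prophylaxis inside the serious-infection event definition, which is not a patient factor.

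3. **What if the 7.3.6 data were meant?** The three SAP items follow the order of the three categories in 7.3.6, so this is plausible. A timing gap then appears. The 7.3.6 window covers follow-up as well as the run-in, so *present* could include prophylaxis begun on treatment, even after the event being analysed. The SAP sets timing rules for comparable items: prior medications must have started by the day before treatment (8.2.2), and concomitant drugs used after first onset are left out (8.2.3.1). It sets none for these three factors beyond the word *prior*.

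4. **Which timing rule suits the planned analysis?** The risk ratios in 8.1.3 and 8.2.3.3 compare crude proportions. If *present* meant started before the event, event-free patients would have all of follow-up in which to become *present*, while patients with an event would have only the time to onset. That is immortal-time bias, and it would make prophylaxis look protective. A cut-off at Day 1 avoids it.

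**The case against.** The strongest reply is that this is only a label. The three diseases and their order match protocol 7.3.6, and the SAP is an English translation of a Japanese original, so the prophylaxis data may well be what the authors intended. Neither the CRF nor the Japanese text is among the documents. This stands, and it limits what can be claimed.

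- A reader might infer that the three factors are empty, that every patient would be coded *absent*, or that the prophylaxis data are wholly unused. The documents do not show this. It follows only on a literal reading, and even then SAP 7 treats missing categorical items as *unknown*, does not impute missing covariates in univariate analyses, and gives them an *unknown* category in multivariate ones.
- A reader might infer that a serious-infection regression is mis-specified. SAP 6.4 lists candidate covariates, but no section of 8.1 or 8.2.3 specifies a model that uses them. The specified route is the crude risk ratio in 8.2.3.3, with its threshold of 10 patients.
- No risk ratio specific to tuberculosis or Pneumocystis pneumonia is planned, because both sit inside the serious-infection composite. Hepatitis B reactivation is not one of the three outcomes in 6.4.
- The applied/not-applied marks for these rows of the 6.4 table cannot be read in the available text, so the outcomes to which each covariate was assigned are unknown.

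The reply does not remove the need for a correction. On the literal reading the source is missing; on the mislabel reading the label is wrong and the timing rule is missing.

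**Conclusion.** The plan is wrong as written on this point and should be corrected. Three of five vaccination factors, on six SAP lines, do not correspond to any vaccination item in the protocol, and the prophylaxis that the protocol does collect for those diseases has no named analysis. The finding rests on protocol 7.3.5, 7.3.6 and Table 2 as the description of what is collected; a CRF with extra vaccination fields would change it.

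The effect on any estimate cannot be quantified. The documents give no rate of prophylaxis use, and it is not known which elements of the safety specification will reach 10 patients with events. Correct labelling would not make the ratios causal either: prophylaxis may go preferentially to patients at higher risk, so confounding by indication remains and the ratios should be read with caution.

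**What to change.** In both SAP 6.4 and SAP 8.2.2, replace the three lines by:

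- *Prior prophylactic treatment for tuberculosis [absent, present]*
- *Prior prophylactic treatment for Pneumocystis jirovecii pneumonia [absent, present]*
- *Prior prophylactic treatment for hepatitis B [absent, present]*

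In 6.4, keep *absent* as the reference. Name protocol 7.3.6 as the source. Define *present* only as prophylaxis started on or before Day 1, and do not use a started-before-the-event definition in the crude risk ratios. Add a sentence that the ratios for these factors are open to confounding by indication.

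If the Japanese SAP already says prophylactic treatment, correct the translation and add the source and the Day 1 rule.

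The cost is six SAP lines and a short definition. The protocol already requires the data, so no new collection is needed. The one assumption is that the recorded treatment duration lets the start date be placed relative to Day 1, which should be confirmed against the CRF.
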